The overall goal of this study is to open up the promising treatment of repetitive transcranial magnetic stimulation (rTMS), which has been shown to be effective against seizures in patients with surface neocortical foci, to a much larger population of patients with mesial temporal lobe epilepsy (MTLE) and other forms of epilepsy with deep foci, who are not currently considered good rTMS candidates. We plan to recruit thirty subjects with MTLE from our Comprehensive Epilepsy Center and through referrals from other clinicians. Subjects will undergo a series of noninvasive investigations, including high-resolution brain MRI, EEG, and rTMS. We plan to obtain blood oxygenation level-dependent (BOLD) functional magnetic resonance (MR) images in 30 patients with refractory MTLE during the task-free resting state. We will create a map for each patient of selected neocortical foci that are highly correlated and anti-correlated to the epileptogenic MTL by using a population-based map of normal resting-state MTL connectivity as a seed network of interest. We will conduct a controlled assessment of two different rTMS protocols applied to specific cortical targets (derived from connectivity imaging results) in the 30 patients with medically refractory MTLE. We will randomize subjects into three treatment groups: In Group 1, we will target low-frequency rTMS to cortical regions that are highly correlated with the epileptogenic MTL. In Group 2, we will target high-frequency rTMS to cortical regions that are highly anti-correlated with the epileptogenic MTL. Group 3 will receive sham rTMS as a control intervention. At 12-week follow-up, outcome measures will be seizure frequency (primary) and interictal epileptiform discharge (IED) frequency (secondary). All subjects will have EEG recordings prior to the first TMS session, after the last session, and at 12-week follow-up. Subjects will be blinded to their treatment group assignment. Subjects and family members or caregivers will be asked to maintain diaries of all seizures and possible adverse effects, which will be reviewed by an investigator blinded to treatment group assignments. For each subject, the MRI will be performed in one 1-hour session on one day, the EEGs will be performed in three 1-hour session on three separate days (pre-rTMS, post-rTMS and 12 weeks after rTMS) and rTMS will occur over ten daily 30-minute sessions.

Overall Study Design

Subject Enrollment

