We expect to downmodulate the excitability of the epileptogenic MTL, thus reducing seizure and IED frequency. Although it is difficult to predict the magnitude of such an effect given the unique nature of our targeting based on connectivity findings, prior rTMS studies in epilepsy have shown seizure frequency reductions in the 53-80% range, durable over at least eight weeks of follow-up, and IED frequency reductions in the 14-66% range.^{4,5} Our use of EEG recordings immediately pre- and post-rTMS, as well as at the end of the follow-up period, will allow for an estimation of immediate and delayed/durable effects on the epileptic state in these patients. We expect our results to prove the principle that patients with deep seizure foci can be safely treated by targeting accessible cortical regions and to provide guidance on which active rTMS protocol (high- or low-frequency) is optimal for MTLE.

Our analysis following the second rTMS protocol, in those subjects who participate in that portion of the study, will provide further evidence of the relative efficacy of the two rTMS protocols in downmodulating cortical excitability.

Brain image acquisition

Anatomical and functional connectivity MR images will be acquired using a dedicated research 3.0-Tesla magnet (General Electric Signa VH/i, GE Healthcare, Waukesha, WI) with a commercial head coil. Highresolution structural whole-brain images will be acquired using a T1-weighted sequence with 128 slices per slab, a 256 x 256 matrix, a field of view (FOV) of 256 mm, a slice thickness of 1.33 mm with 0.63 mm interslice gap, repetition time (TR) of 2530 ms, inversion time of 1100 ms, echo time (TE) of 3.39 ms, and flip angle of 7 degrees. Resting-state functional image acquisition will be performed while subjects are asked to rest quietly (acquisition time 6.4 min), using an echo-planar sequence sensitive to BOLD contrast with TR 6000 ms, TE 30 ms, FOV 256 mm, voxel size 2.0 x 2.0 x 2.0 mm, and flip angle 90 degrees.

Functional connectivity analysis

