2. TMS produces a loud clicking sound when the current is passed through the stimulation coil. This loud click can result in ringing in the ears and short-term decreased hearing if no protection is used. In order to prevent this potential adverse effect, subjects will be given earplugs. Animal and human studies have demonstrated that earplugs can effectively prevent the risk of hearing disturbance due to TMS.

In one case a subject's hearing protection fell out and resulted in permanent hearing loss during a 1Hz rTMS session at 120% of the motor threshold. The authors were using a special TMS coil called the H-coil in which the subject's head is inside a large helmet. However, the authors claimed that the loudness of the H-Coil they were using was not different from other coils.¹⁶

In order to better inform and protect the subjects, we will take the following precautions:

- a. Advise subjects of the risk of permanent hearing loss if an earplug should loosen, become detached, or fall out.
- b. Advise subjects that they should immediately report to the investigator any loosening or detachment of an earplug during TMS.
- c. Inform subjects that investigators will immediately stop TMS if the subject reports or if an investigator observes that an earplug has loosened or has fallen out.
- d. Prompt referral for auditory assessment of all individuals who complain of hearing loss, tinnitus, or aural fullness following completion of TMS.

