3. The risk of seizure during TMS is a well-studied one. In normal subjects, it is an extremely rare occurrence. Repetitive TMS can induce a seizure in the absence of pre-existing brain lesions, epilepsy, or other seizure risk factors, both in patients and healthy subjects. From the several thousands of studies that have used TMS to date, a total of 16 cases have been reported, of which 9 cases occurred after the 1998 safety guidelines. Based on the available data, the reported risk of seizures is less than 1 in 1000 for repetitive TMS. In individuals with a known history of seizures, the occurrence of a seizure temporally proximate to TMS is very uncommon; the overall rate of any seizure associated with single- and paired-pulse TMS in those with known epilepsy is only 0.8-1.8%, and the risk if no changes were made in anticonvulsant medications is only 0.0-0.4%. Similarly, even with rTMS in patients with known epilepsy, the crude risk of seizures associated with TMS was about 1.4%, and almost all seizures were identical to those typically experienced by the individual, making it unclear whether seizures were causally related to the TMS or not.¹⁷ Almost all reported seizures predated the advent of current safety guidelines, to which our proposed study will adhere closely. No instances of status epilepticus have ever been reported in association with TMS.
4. Syncope can occur due to anxiety and psycho-physical discomfort during testing and treatment with TMS. This is reported less than seizure activity but the true number may be higher due to underreporting. Subjects will be monitored for feeling any signs or symptoms of a pending syncopal event (i.e. feeling "dizzy, lightheaded or going to pass out"). TMS will immediately be stopped and the subject will be assisted.
5. TMS could induce short-term changes in memory, attention, and other cognitive functions. This is a theoretical risk, as none of the safety studies conducted has found such side effects. However, because the understanding of brain connectivity in the population of patients with PNH is limited, the risk for these patients in particular is not clear.

6. Acute psychiatric effects such as mania and delusions have been described in patients with medically refractory depression or bipolar disorder who received rTMS. This seems to be a rare complication (incidence <0.15% of patients), and individuals with a current diagnosis of a mood disorder will be excluded from this study.

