7. The possibility of dental pain during rTMS has been reported. This potential adverse effect would occur during the stimulation itself. Subjects will be asked to report any such discomfort immediately to the investigator, who would terminate the stimulation session. The subject will be encouraged to seek a dental evaluation, since this is a very rare occurrence but may point to the presence of a cavity that may require care. This adverse effect is not expected to lead to any lasting problems or complications.

Protection Against Risks

As described above, no significant health risks are expected from the neuroimaging procedures in this study. Standard research MRI safety procedures in place at Beth Israel Deaconess Medical Center will be used, including safety questionnaires prior to scanning (asking about surgeries, metal implants, shrapnel, etc.).

Multiple safety precautions are in place for the TMS portion of the study, including the design of the stimulation protocol in a way that is well within guidelines for rTMS safety, is consistent with prior studies that have demonstrated safety in a population of patients with refractory epilepsy.⁴ All TMS sessions will be conducted in the presence of a board-certified neurologist who has been trained in the safe and efficient administration of TMS and in basic life support and in the recognition and treatment of seizures, syncope, and other neurological and medical emergencies. A fully equipped and regularly checked “crash cart” is available at Beth Israel Deaconess Medical Center for potential emergencies. This emergency equipment also includes oxygen supply, IV line supplies, and emergency medications in the event of a convulsion. Subjects will be monitored in detail during and after delivery of TMS, using an approach drawn directly from suggested guidelines.

Confidentiality will be preserved at all times, using standard HIPAA-compliant clinical measures already in place at the institution. As described above, only the PI and PI's research assistant will be aware of individual subject identities and have access to code number assignments.

The PI, a board-certified neurologist and clinical neurophysiologist, will be responsible for the patient's medical welfare should any unexpected adverse events occur during these research activities, and will intervene as appropriate.

Risk-Benefit Analysis

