Given the limited foreseeable risks described above, the procedures to be put in place to protect against these risks, and the potential benefits to the subjects and others as described above, the risk/benefit ratio is acceptable for subjects.

Data and Safety Monitoring

All adverse effects, regardless of attribution to study procedures, will be collected from the start of the experimental protocol to the end of study participation, using standard adverse event forms. Subjects will be asked in an open-ended way about the presence of any adverse events; intensity will be graded

for each adverse event; and the likelihood that the event is or is not related to study participation will be noted.

A data safety monitoring board, comprising three investigators with expertise in the field, experience in conduct of human subject research and statistical knowledge, independence from the direct management of this study, and freedom from conflict of interest or commitment, will be appointed by the PI. A chairperson will be appointed and will be responsible for overseeing the meetings, developing the agenda, and summarizing the meeting. The chairperson will be the contact person for the DSMB.

The DSMB will meet prior to the enrollment of the first subject to review the research protocol, informed consent documents and plans for safety and data monitoring of the study. The DSMB will determine the risks and benefits to research subjects, protection and safety of the subjects and offer suggestions for improving the study design. In addition, the Board will reach agreement on the data that will be required for review. Determination of the schedule of future meetings, appointment of the chair and voting members, who receives minutes, and the signing of conflict of interest statements will occur during pre-enrollment meeting. The pre-enrollment Board meeting may result in modification of the safety plan provided in the CCI application. If the DSMP is changed at the first meeting of the Board, the new plan will be submitted to the BIDMC Committee on Clinical Investigations (CCI).

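### Staff ask about adverse events in an open-ended way, with no directed question for cognitive, psychiatric, or headache and neck-pain effects, so these may be under-recorded

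*Combined protocol and SAP*

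**What the plan says.** All references are to the combined protocol and SAP.

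- **Scope of collection (B5, Data and Safety Monitoring).** "All adverse effects, regardless of attribution to study procedures, will be collected from the start of the experimental protocol". Standard forms are used, and intensity and likely relatedness are noted.
- **How staff ask (same section).** "Subjects will be asked in an open-ended way about the presence of any adverse events". No list of symptoms to ask about is given.
- **Diaries (B3.A Overview and Subject Enrollment; B3.C).** "Subjects and family members or caregivers will be asked to maintain diaries of all seizures and possible adverse effects". A blinded investigator reviews them.
- **Observation at sessions (B5, Protection Against Risks).** "Subjects will be monitored in detail during and after delivery of TMS, using an approach drawn directly from suggested guidelines". A neurologist is present at every session.
- **Named risks (B5, Transcranial magnetic stimulation, items 1 to 7).** Headache or neck pain, hearing, seizure, syncope, cognitive change, acute psychiatric effects and dental pain. For syncope: "Subjects will be monitored for feeling any signs or symptoms of a pending syncopal event". For hearing, one of the precautions is: "Prompt referral for auditory assessment of all individuals who complain of hearing loss, tinnitus, or aural fullness following completion of TMS".
- **Cognitive risk (item 5).** After a general statement about TMS, the item ends: "because the understanding of brain connectivity in the population of patients with PNH is limited, the risk for these patients in particular is not clear". Eligibility in B3.C requires MTLE.
- **Expected conclusion (B3.B, Data Analysis).** The results are expected to prove the principle that "patients with deep seizure foci can be safely treated by targeting accessible cortical regions".

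**The concern.** B5 identifies seven harms, but the stated way of asking about them names none. An open question works best for events that are salient to the subject or visible to staff. A change in memory, attention or mood that develops between visits during the 12-week follow-up is neither reliably salient nor visible in the stimulation room. If such changes are not mentioned, the record shows nothing, and an empty record may be read as evidence of safety. The monitoring board's review of aggregate adverse events would draw on the same record.

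The protocol itself accepts that this can happen. Its syncope item says the reported frequency may be too low because events go unreported, and it answers with monitoring for named symptoms. The cognitive item has no equivalent step, although the intervention aims to alter excitability in the mesial temporal network.

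**Working it through.** **Step 1: set each named harm against its collection route.** The general open question, the diaries and session monitoring apply to all seven. The table shows what is added for each.

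| Harm (B5 item) | Additional step | Directed question, scale or test |
|---|---|---|
| Headache or neck pain (1) | Acetaminophen offered | None |
| Hearing (2) | Earplug advice, stopping if a plug loosens, referral after a complaint | None; referral waits for a complaint |
| Seizure (3) | Counted by diary as the primary outcome | Counted directly |
| Syncope (4) | Named warning symptoms monitored | In effect, yes |
| Cognitive change (5) | None | None |
| Psychiatric effects (6) | Current mood disorder said to be excluded | None |
| Dental pain (7) | Subjects asked to report it at once | In effect, yes |

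The gap is therefore items 1, 5 and 6, with item 2 partly covered. On item 6, the numbered exclusion list in B3.C does not name mood disorder, so the two sections should be reconciled.

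**Step 2: is there a figure in the plan to reproduce?** No. B3.B sets out no adverse-event analysis, by arm or otherwise, and no section gives a capture rate.

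**Step 3: illustration under assumed capture.** With 30 subjects in three equal groups, each arm has 30/3 = 10, so 20 are active. If a harm has true incidence p and a fraction s of cases is recorded, then

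P(at least one recorded among 20) = 1 − (1 − p·s)^20.

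Every s below is an assumption, as are the 5% and 10% incidences.

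| s | p = 10% | p = 5% |
|---|---|---|
| 1.00 | 0.88 | 0.64 |
| 0.90 | 0.85 | 0.60 |
| 0.50 (0.40 to 0.60) | 0.64 (0.56 to 0.71) | 0.40 (0.33 to 0.46) |
| 0.25 | 0.40 | 0.22 |

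Worked case: p = 0.10 and s = 0.50 give 1 − 0.95^20 = 0.64.

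For headache or neck pain the protocol gives a rate of up to 20–40%. Expected recorded cases among 20 are 20 × 0.20 = 4 to 20 × 0.40 = 8 with full capture, and 2 to 4 if half are captured.

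**Step 4: what sample size alone allows.** With zero events and full capture, the one-sided 95% upper bound is 1 − 0.05^(1/n):

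- n = 20: 13.9%
- n = 10: 25.9%

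For psychiatric effects, the protocol's rate is below 0.15%. Taking 0.15% as the ceiling, the chance of seeing at least one case in 20 is 1 − 0.9985^20 = 0.03 with full capture and about 0.015 at half capture. For a harm that rare, the way of asking makes almost no practical difference.

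**Step 5: the PNH sentence.** Item 5 describes uncertainty for PNH, while B3.C enrolls on a diagnosis of MTLE. This is an error in the description of risk. It does not change how any event is found or counted.

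**The case against.** The strongest reply is that the open question is one of several sources. Caregivers as well as subjects keep diaries that cover adverse effects, a blinded investigator reads them, and a neurologist attends each session. The content of the standard forms is not shown and could include prompts. The monitoring board agrees its data requirements before enrollment, may change the safety plan then, and reviews the quality of the collection forms. Item 5 describes cognitive risk as theoretical, and its opening sentence applies to any TMS subject. Prompting also raises reports of minor complaints, and a yes/no memory item is still self-report.

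Much of this stands. A reader might infer that adverse events are found only through the open question, or that every harm named in B5 will be under-counted. The documents support neither reading: the other sources exist, and seizure, syncope and dental pain have their own steps. A reader might also link the PNH wording to lost events, or conclude that no PNH patient could be enrolled. The wording cannot affect counts, and PNH is not a listed exclusion; it is simply not the target population. Nor do the documents specify a safety comparison between arms that would be biased. The conclusion about safe treatment is an expectation, not a planned test.

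What the reply does not remove is the absence of any directed question for three named harms. That the board might alter the plan is not a specified procedure.

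**Conclusion.** The point holds in limited form. Cognitive change, psychiatric effects, and headache or neck pain depend on volunteered reports, diaries and general observation, and hearing referral depends on a complaint. These harms may be under-recorded; the documents do not show that they will be. The tabulated probabilities show how sensitive a group of 20 is to imperfect capture, but they rest on assumed capture rates and incidences and are not an estimate for this trial.

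The benefit of better questioning lies with harms of moderate frequency. For very rare harms, sample size limits the safety conclusion more than the form of the question does. This is a worthwhile, inexpensive improvement and does not affect the efficacy design. The PNH sentence is a separate text correction.

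**What to change.** In B5, Data and Safety Monitoring:

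1. Keep the open question and ask it first.
2. Follow it with a short fixed checklist of the B5 harms, including memory and attention, mood, hearing, and headache or neck pain.
3. Ask it in identical words in all three arms at the ten rTMS sessions and at the post-rTMS and 12-week EEG visits (10 + 2 = 12 occasions per subject).
4. Record volunteered and prompted events separately.
5. Add to B3.B a table of each by arm with exact intervals, so that zero counts are reported with their upper bounds.

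The cost is a one-page form and, on a working assumption, a couple of minutes at visits already planned. The downside is that more minor complaints will be recorded in every arm, including sham. The sham arm gives the reference for reading them, and separate recording preserves the volunteered rate. A checklist will not measure cognition objectively; that would need a test before and after rTMS, a larger change than is proposed here.

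Separately, reword the last sentence of B5 item 5 for the MTLE population and check that the consent form, which is not in view here, matches.
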